2.2 Secondary Efficacy Endpoints (52-week)

- i) Mean percent absolute weight loss in the AT group compared to the Control group
- ii) Proportion of subjects who achieve ≥10% absolute weight loss in the AT group compared to the Control group

The percent change in the AT Group compared with the percent change in the Control Group will be assessed for the following variables:

- iii) Serum triglyceride, HDL-cholesterol and LDL-cholesterol concentration
- iv) Systolic and diastolic blood pressures
- v) "Impact of Weight on Quality of Life" (IWQOL) questionnaire
- vi) Hemoglobin A1C (for subjects with T2 diabetes at screening only)
- vii) mean percent change in medications

In the AT group only:

viii) Procedural success defined as successful endoscopic placement of the A-TubeTM in all subjects undergoing endoscopy

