4.0 Study Population & Recruitment

The study population is 175 obese men and women who (i) have a Body Mass Index (BMI) between 35.0 and 55.0 kg/m², (ii) are 21-65 years old, and (iii) have failed to achieve and maintain weight loss with non-surgical weight loss therapy.

Subjects will be enrolled at 8-12 sites within the United States. Each site is encouraged to enroll, on average 15 subjects (i.e. 10 treatment group and 5 control group) and no fewer than 10 subjects. No site may enroll more than (30) subjects.

Randomization will be stratified for both initial BMI and sex to help ensure equal number of males in both the therapy and control group and to guarantee that extremely obese subjects (BMI >40 kg/m²) are equally distributed between the study groups. Initial BMI, sex, and race will be compared between study groups and adjusted in the analysis as covariates if an imbalance is found between groups.

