4.2 Exclusion Criteria

- 1. Previous abdominal surgery that significantly increases the medical risks of gastrostomy tube placement
- 2. Esophageal stricture, pseudo-obstruction, severe gastroparesis or gastric outlet obstruction, inflammatory bowel disease
- 3. History of refractory gastric ulcers
- 4. Ulcers, bleeding lesions, or tumors discovered during endoscopic examination.
- 5. History of radiation therapy to the chest or abdomen
- 6. Uncontrolled hypertension (blood pressure >160/100).
- 7. Diabetes treated with insulin or sulfonylurea medications
- 8. Any change in diabetes medication in previous 3 months
- 9. Hemoglobin A1C >9.5%
- 10. History or evidence of serious pulmonary or cardiovascular disease, including acute coronary syndrome, heart failure requiring medications, or NYHA (New York Heart Association) class III or IV heart failure (defined below):

Class III: patients with marked limitation of activity and who are comfortable only at rest

Class IV: patients who should be at complete rest, confined to bed or chair and who have discomfort with any physical activity

- 11. Coagulation disorders (platelets < 100,000, PT > 2 seconds above control or INR > 1.5)
- 12. Anemia (Hemoglobin <11.0 g/dL in women and <12.5 g/dL in men)
- 13. Liver enzymes (ALT and AST) ≥3.0 times the upper limit of normal
- 14. Thyroid Stimulating Hormone (TSH) >1.5 x upper limit of normal at screening.
- 15. Osteoporosis (DEXA T-Score \leq -2.5 standard deviations below normal peak values).
- 16. History of fragility fractures (fractures resulting from a fall from a standing height or less, or presenting in the absence of obvious trauma)
- 17. Pregnant or lactating
- 18. Diagnosed Bulimia or diagnosed Binge Eating Disorder (using DSM IV criteria)
- 19. Night Eating Syndrome (diagnosed by EDE)
- 20. Serum potassium < 3.8 mEq/L
- 21. Chronic abdominal pain that would potentially complicate the management of the device
- 22. Taking a GLP-1 agonist < 6 months.
- 23. Taking prescription or over-the-counter medications for weight loss in the last 3 months before screening, or planning to participate in a commercial weight loss program in the next 24 months. This includes taking medications for an unrelated medical condition which have been shown to result in weight loss such as Topiramate or Bupropion.

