5.2 Randomization

Eligible subjects who fulfill all enrollment criteria obtained during Screening will be randomized to the Treatment or Control Group in a 2:1 ratio, stratified by sex and BMI (< or ≥ 40.0 kg/m2) at each study site. A web-based randomization scheme will be established to ensure there is no possibility that group assignment can be known in advance. To avoid temporal bias, randomized blocks of varying sizes will be used to prevent investigators from having advanced knowledge of the assignment of the last subject in a given block. Randomization will occur within 14 days of the screening visit. Subjects will be notified by telephone of their group assignment.

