8.5.4 Secondary Efficacy Endpoints

The percent change from baseline will be calculated for all major time points and the results will be summarized for each group. Within treatment group differences will be tested using a Students T-test for paired samples on the percentage change from baseline at each study visit. Difference between treatment groups will be tested by using the two-sample t-test or Wilcoxon Test whenever appropriate.

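### The between-group tests of lipids, blood pressure, IWQOL and HbA1c are valid but leave out each outcome's own collected baseline as a covariate, which costs precision and exposes the HbA1c subset to chance imbalance

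*Protocol*

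**What the plan says.** Section 2.2 defines the comparison for serum lipids, systolic and diastolic blood pressure, IWQOL, HbA1c and medications: "The percent change in the AT Group compared with the percent change in the Control Group will be assessed for the following variables". HbA1c is limited to a subset: "Hemoglobin A1C (for subjects with T2 diabetes at screening only").

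Section 8.5.4 repeats the scale ("The percent change from baseline will be calculated for all major time points and the results will be summarized for each group") and names the between-group test: "Difference between treatment groups will be tested by using the two-sample t-test or Wilcoxon Test whenever appropriate". It names no covariate.

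Two other places mention adjustment. Section 4.0 says that initial BMI, sex and race will be compared between groups and "adjusted in the analysis as covariates if an imbalance is found between groups". Section 8.5 plans a covariate analysis with race, age, gender and initial BMI, for the two primary endpoints. Neither lists a secondary outcome's own baseline.

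Those baselines are collected. Tables 1 and 3 schedule the lipid panel, HbA1c and IWQOL at screening in both arms, and the screening examination in section 5.1 includes blood pressure.

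Under section 5.2, randomisation is "stratified by sex and BMI (< or ≥ 40.0 kg/m2) at each study site". Diabetes is not a stratification factor.

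**The concern.** Baseline enters the analysis only as the denominator of the percent change. Division does not remove its influence. Subjects who start high tend to fall and those who start low tend to rise, in both arms, so percent change stays negatively correlated with baseline. Two things follow.

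- **Precision.** The variation explained by baseline stays in the error term, so the intervals are wider than the collected data require.
- **Chance imbalance.** If one arm happens to start higher, part of its later fall is counted as treatment effect.

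The second matters most for HbA1c. The subset is restricted to type 2 diabetes and cut further by the exclusion "Diabetes treated with insulin or sulfonylurea medications". Its size is not stated, and its balance between arms is not protected by stratification. These comparisons are the trial's randomised evidence on metabolic, blood pressure and quality-of-life effects. An adjustment chosen only after an imbalance is seen would be open to challenge.

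**Working it through.** **The plan's own figures.** The protocol gives no sample size, SD, correlation or power for these outcomes, and no size for the diabetes subset, so there is no stated figure to reproduce. The inputs taken from the protocol are 117 AT and 58 Control enrolled, and drop-out of 10% and 20% (sections 8.1.1 and 8.1.2). Everything else below is an assumption, shown over a range.

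**1. Precision, simple change score.** Let the baseline and week-52 values have equal SD σ and correlation ρ.

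- Variance of unadjusted change: 2σ²(1−ρ)
- Residual variance after adjusting for baseline: σ²(1−ρ²)
- Ratio, adjusted to unadjusted: (1−ρ²) / [2(1−ρ)] = (1+ρ)/2

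| ρ (assumed) | variance ratio | interval width ratio (square root) |
|---|---|---|
| 0.3 | 0.65 | 0.81 |
| 0.5 | 0.75 | 0.87 |
| 0.7 | 0.85 | 0.92 |
| 0.8 | 0.90 | 0.95 |

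Adjusted intervals would be about 19% narrower at ρ = 0.3 and 5% narrower at ρ = 0.8.

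**2. The same check on percent change.** Section 8.5.4 tests percent change, not simple change, so the formula is only a guide. Simulation (3,000 trials per case) compared the unadjusted percent-change difference with ANCOVA of percent change on baseline.

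- Systolic pressure, 117/58, assumed mean 130, SD 15, effect −5. The standard error falls from 1.89 to 1.64 at ρ = 0.5 (variance ratio 0.75), from 1.49 to 1.39 at 0.7 (0.86), and from 1.19 to 1.15 at 0.8 (0.93).
- HbA1c, assumed subset 18/9, mean 7.0, SD 0.9, effect −0.5. The standard error falls from 5.95 to 5.05 percentage points at ρ = 0.4 (0.72), from 4.80 to 4.37 at 0.6 (0.83), and from 3.31 to 3.25 at 0.8 (0.96).

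The results agree with the formula in direction and roughly in size. At ρ = 0.8 the gain nearly disappears.

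**3. Chance imbalance in the HbA1c subset.** Completers: 117 × 0.90 ≈ 105 AT and 58 × 0.80 ≈ 46 Control. In SD units, the standard error of the baseline difference is √(1/n₁ + 1/n₀).

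| Assumed share with T2 diabetes | n₁/n₀ | SE (SD units) | P(difference > 0.5 SD in either direction) |
|---|---|---|---|
| 10% | 10/5 | 0.55 | 36% |
| 20% | 21/9 | 0.40 | 21% |
| 30% | 32/14 | 0.32 | 12% |

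A baseline difference d shifts the unadjusted change-score difference by −(1−ρ)d. For d = 0.5 SD that is 0.35 SD at ρ = 0.3, 0.25 SD at 0.5 and 0.10 SD at 0.8.

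On the percent-change scale, in the simulated 18/9 subset, each 1-point imbalance in baseline HbA1c moves the estimate by 8.8, 5.8 or 2.6 percentage points at ρ = 0.4, 0.6 or 0.8. The SD of the imbalance is about 0.37 points (0.9 × √(1/18 + 1/9)). A one-SD imbalance therefore moves the estimate by about 3.3, 2.2 or 1.0 percentage points, against an average simulated effect of about −7.

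**The case against.** The strongest reply is that little depends on these tests. Section 8.1.3 says that secondary results will only appear in data tables, will not count as statistical proof of efficacy, and will support no labeling claim. That stands, and it limits the consequence. It does not remove the point: section 8.5.4 still prescribes between-group tests, section 8.2 sets a 5% level for all tests and intervals, and a descriptive estimate is also better for being precise.

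A second reply is that the adjustment clause in section 4.0 is not confined to the primary endpoints, and that the baseline tables in section 8.3 may reveal imbalance. Both are true. The clause covers only BMI, sex and race, however, and seeing an imbalance does not adjust for it.

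A third is that covariate models are often left to a statistical analysis plan. One may exist and may specify ANCOVA. Here, though, the protocol itself names the test.

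A reader might infer more: that the tests are invalid, that they inflate type I error, or that the HbA1c result will be biased. The documents do not support this. Under randomisation the unadjusted comparison has no systematic bias from baseline differences, and the missing covariate does not inflate type I error. The imbalance effect is conditional on what chance produces and averages to zero. Nor is baseline ignored altogether, since it is the denominator of the endpoint. A reader might also infer a risk to trial success, but success rests on the two primary endpoints alone.

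**Conclusion.** The point holds as a modest improvement to a stated method, not as the correction of an error. Section 8.5.4 fixes an unadjusted test of percent change for four groups of outcomes whose baselines are already measured in both arms, and no other section supplies adjustment for those baselines.

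The unadjusted analysis carries about 1.1 to 1.5 times the variance of the adjusted one (1/0.90 to 1/0.65), under assumed correlations of 0.8 down to 0.3, equal variances and a simple change score. At a correlation of 0.8 the gain is small, and in a small HbA1c subset it is negligible. The exposure to chance imbalance is greatest for HbA1c, but its size depends on a subset size and a correlation that the protocol does not give. Because the secondary results are tabulated without claims, no trial decision changes.

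**What to change.** In section 8.5.4, for lipids, blood pressure, IWQOL and HbA1c:

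- Keep the percent change of section 2.2 as the endpoint. Compare groups at week 52 by ANCOVA with treatment, that outcome's own baseline value (the one used as the denominator), sex and BMI stratum (<40, ≥40 kg/m²). Report the adjusted difference with its 95% CI.
- For skewed outcomes such as triglycerides, specify a rank-based or log-scale version of the same model.
- For HbA1c, fit the model within the type 2 diabetes subset with baseline HbA1c as covariate, and allow the strata to be dropped if the subset is small. The synopsis words this endpoint as a change in the mean and section 2.2 as percent change. State one scale; the covariate is the same for either.
- Show the unadjusted comparison alongside.
- Leave the percent weight loss and medication endpoints as they are.

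Keeping percent change avoids a conflict between the test and the endpoint definition in section 2.2. The cost is a wording change and a little more analysis work, with no new data, visits or subjects. The drawback is that the main estimate becomes an adjusted rather than a raw difference, which is why the raw one should stay in the table.

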9.0 Quality Control and Quality Assurance Procedures

9.1 Data Quality Assurance

Steps taken to assure the accuracy and reliability of data include review of protocol procedures with the investigators and associated personnel prior to the study and a monitoring visit by Aspire Bariatrics Clinical Monitor to each clinical site. Electronic case report forms will be reviewed for accuracy and completeness as compared with the source documents.

9.2 Monitoring

The study will be initiated by the medical monitor (or designee) during an on-site visit after all required documents have been processed. Monitoring will be performed during the study to verify that the rights and well-being of the subjects are protected, the trial is conducted according to Good Clinical Practices (GCP), the protocol and applicable amendments are followed, and the recorded data is accurately represented according to the source documentation.

9.3 Protocol Modifications

Protocol modifications must be evaluated against FDA guidelines to determine whether prior approval is required, or 5 day notification or inclusion in annual report is sufficient.

Prior to initiating any protocol modification, the site's IRB will approve such protocol modification.

All protocol amendments must be signed and dated by the investigator prior to implementation of the amendment.

In situations requiring departure from the protocol, the investigator or other physician in attendance will contact the assigned medical monitor by fax or telephone (**Appendix L**). If possible, this contact will be made before implementing any departure from the protocol. In all cases, contact with the medical monitor must be made as soon as possible in order to discuss the

situation and agree on an appropriate course of action. The CRF and source document will describe any departure from the protocol.

9.4 On-Site Audits

A Clinical Monitor, a trained and properly authorized employee of Aspire Bariatrics, may request access to all study records, including source documents, for inspection and copying. The study site will be expected to provide adequate monitoring facilities, with appropriate computer connections and work space.

10.0 Ethics and Regulatory Considerations

This study will be conducted in accordance with Good Clinical Practices and any local regulations.

10.1 Institutional Review Board/Medical Ethics Committee

The protocol will be submitted to an Institutional Review Board (and /or Medical Ethics Committee or similar body if required by local regulations) for approval prior to initiation of the study.

10.2 Informed Consent

Each subject (or legally authorized representative) shall sign and date a current informed consent (see **Appendix M**) (and other locally required documents) after the nature of the study has been fully explained. If a protocol amendment results in a change in the Informed Consent Form, a new Informed Consent Form approved by the study site Institutional Review Board will be signed by all subjects.

10.3 Clinical Investigator

The investigator selected for this clinical study will be responsible for following the protocol and providing both procedural and follow-up data.

The investigator must also:

- Agree to the requirements of this protocol by signing the Protocol Signature Page.
- Obtain subject informed consent according to local regulations.
- Provide the required data on the case report form as soon as it becomes available.

10.4 Confidentiality

Research records are marked by subject number and initials. Subject identifiers/linking information will be kept in a locked location separate from the research records. Subject identifiers will not be stored on any network drive. Subject research files, including signed consent forms, will be kept in locked storage area at the study site. All information provided to the Investigator by the Sponsor, or its designates, including non-clinical data, protocols, CRFs, and verbal and written information, will be kept strictly confidential and confined to the research staff involved in conducting the study. It is recognized that this information may be related in confidence to the Institutional Review Board. Subjects' records will be made available to the Sponsor's Clinical Monitors and regulatory authorities as required.

11.0 Record Keeping/ Reporting

11.1 Required Documents

The following documents shall be submitted to Aspire Bariatrics prior to study initiation:

- Signed and dated Protocol Signature Page.
- A copy of the formal written notification of the IRB or similar body to the investigator regarding approval of the protocol.
- A copy of the informed consent form to be used in the study.
- All local regulations must be met and the necessary documentation submitted to Aspire Bariatrics.

In addition to the documents required prior to the study, other documentation may be required during the course of the study.

11.2 Case Report Forms

Data will be entered promptly into electronic case report forms (**Appendix** N). The case report form must be electronically signed and dated by the principal investigator or designated research team member.

11.3 Record Retention

All case report forms and all source documents (i.e., laboratory reports, progress notes, medical histories, physical and diagnostic findings, diagnoses and procedure dates, device disposition records) that support case report forms of each subject must be retained in the files of the responsible investigator for a minimum of seven years following notification by Aspire Bariatrics that all investigations of the device have been completed or discontinued.

If the responsible investigator retires, relocates, or for other reasons withdraws from the responsibility of keeping the study records, custody must be transferred to a person who will accept the responsibility. Aspire Bariatrics must be notified in writing of the name and address of the new custodian.

11.4 Use of Information and Publication

All information concerning Aspire Bariatrics' operations, patent application, manufacturing processes, and basic scientific data supplied by Aspire Bariatrics to the investigator and not previously published, are considered confidential and remains the sole property of Aspire Bariatrics. The investigator agrees to use this information only to accomplish this study and will not use it for other purposes without the written consent of Aspire Bariatrics. This includes releasing any information or comments to the media.

The investigator understands that the information developed in the clinical study will be used by Aspire Bariatrics and may be disclosed as required to other clinical investigators or government regulatory agencies. To permit the information derived from the clinical studies to be used, the investigator is obligated to provide Aspire Bariatrics with all data obtained in the study.

11.5 Reporting

Reporting will be accomplished by using an electronic Case Report Book that can be accessed via the internet by the Sponsor's Clinical Monitors. CRFs shall be completed promptly, including data from screening visits, implantation procedure, Skin-Port installation and all other visits specified in Tables 1-3.

11.6 Study Termination

The Investigator will complete the study and submit the case report forms in accordance with the agreed time frame after receipt of clinical supplies by Sponsor (or satisfactory disposal of such supplies). Either the Investigator or the Sponsor may terminate this study for good and valid reasons prior to its planned conclusion, provided reasonable notice is given in advance of the intended termination.

12.0 Clinical Supplies

Aspire will supply the AspireAssist A-Tube, the AspireAssist Starter Kit, and all AspireAssist accessories to the site.

The A-Tubes is supplied in a sterile package. The A-Tube is not currently packaged with the instruments that are commonly supplied with commercial PEG tubes, such as snares, etc. The site may use the supplies packaged with standard Ponsky-pull method gastrostomy tubes and charge Aspire for such kit. It is anticipated that by approximately April 2013, the A-Tubes will be available with the instruments that are commonly supplied with commercial PEG tubes.

All other components of the AspireAssist are supplied non-sterile as they are not used in an aseptic environment.

All investigational devices received and used by the investigator will be inventoried and accounted for throughout the study. The **AspireAssist Aspiration Therapy System** components will be stored as per the package label in a secure, locked area with restricted access separate from other medical devices.

The investigator agrees not to supply the investigational device(s) to any person except those involved in this study.

12.1 Accountability

A Device Disposition Record must be maintained by each investigator (or designee).

12.2 Instructions for Return of Damaged or Unused Devices

When instructed by Aspire Bariatrics (or designee), the investigator must return any damaged or unused devices to:

Quality Assurance Aspire Bariatrics, Inc. [name]

The Clinical Device Return Form (**Appendix O**) must be completed and returned in the box with the devices. The investigator shall keep a copy of the Clinical Device Return Form.

12.3 Instructions for Return of Used A-Tubes

After withdrawal of a treatment group subject, or potentially at the conclusion of the study, the A-Tube will be removed and, upon request, returned to the company. In addition, the company can require that a displaced A-Tube be returned.

The following procedures must be followed for return:

- Flush the A-Tube with normal (0.9%) saline or lactated Ringer's solution and immediately submerge the device in 10% neutral, buffered formalin.
- Ship the A-Tube in the 10% neutral, buffered formalin solution by using the container supplied by Aspire.
- Fill out the information on the label provided by Aspire, and place the outside of the first level of inner wrap, positioned so that it is seen immediately upon opening. Place cushioning material around inner container.

• Make sure the container is sealed tightly and apply tape around the lids as an extra precaution.

